5.4.2 Antibacterial, Antifungal, and Antiviral Prophylaxis

Broad spectrum antimicrobial prophylaxis should be administered preoperatively according to site-specific standards, or as the Transplant Infectious Disease consultant recommends.

TRIMETHOPRIM/SULFAMETHOXAZOLE (BACTRIM SS® OR SEPTRA SS®)

Trimethoprim/sulfamethoxazole will be administered at a dose of 80 mg/400 mg PO QD starting on Day

+1 for 6 months after islet transplantation for prevention of *Pneumocystis carinii* pneumonia (PCP). In the event that a subject is unable to take trimethoprim/sulfamethoxazole, he/she will be treated on a case-by-case basis as is medically indicated. Side effects of Bactrim include allergic reactions, nausea, vomiting, diarrhea, fulminant hepatic necrosis, and blood dyscrasias (leucopenia, agranulocytosis, aplastic anemia, and hemolytic anemia). Subjects who are allergic to sulfa drugs will receive pentamidine. 300mg of pentamidine will be given via nebulizer once a month after the transplant to prevent PCP. Pentamidine aerosol has the side- effects of metallic taste, fatigue, and decreased appetite.

CLOTRIMAZOLE (MYCELEX TROCHE®)

Clotrimazole will be administered as 1 troche PO QID starting on day -2 relative to initial transplant, day -1 for subsequent transplants, to be continued for 3 months after transplantation. Patients may receive antifungal prophylaxis according to local standard of care.

VALGANCICLOVIR (VALCYTE®)

Valganciclovir is an antiviral drug which will be given to prevent CMV infection starting on Day -2 for initial transplants, Day -1 for subsequent transplants, at a dose of 450 mg PO QD, increasing to 900 mg QD by Day 12 and continuing for 14 weeks posttransplant. If the CMV status of the donor and recipient are both negative, then valganciclovir administration may be adjusted or eliminated. Valganciclovir has the possible side effects of neutropenia and thrombocytopenia, with related risks of infection and bleeding. Frequent cell counts will be performed and the valganciclovir dose adjusted accordingly. Other infrequent (~2%) side effects include low red blood cell count, fever, rash, and an increase in liver enzymes.

5.4.3 Anticoagulation Prophylaxis / Hematological Agents

HEPARIN

Heparin may be administered at a dose of 70 U/kg BW of recipient, divided equally among the islet bags, given with islet transplant, followed by 3U/kg/hr IV for the next 4 hours. From the 5th through the 48th hr post-transplant heparin will be titrated to achieve and maintain PTT between 50-60 seconds. If a site does not use PTT to titrate heparin, a comparable site-specific method and value should be used.

ENOXAPARIN (LOVENOX®)

Enoxaparin will be administered at a dose of 30 mg sc BID through day 7 post-islet transplant, with the first dose given 48 hours after the transplant procedure (when heparin is discontinued). The dose can be modified or extended at the discretion of the investigator.

Dalteparin can be substituted for enoxaparin at the PI's discretion.

ASPIRIN

Enteric coated aspirin will be administered at a dose of 81 mg PO qPM starting 48 hours post-transplant and continued as medically indicated.

PENTOXIFYLLINE (TRENTAL®)

Pentoxifylline will be administered at a dose of 400 mg slow release TID beginning 2 days prior to transplant (Day -2) and continuing for 7 days post-transplant (Day 7). *Pentoxifylline* (Trental®) is indicated as an adjunctive treatment for subjects with claudication and peripheral vascular disease because of its ability to improve blood viscosity. In experimental islet transplantation in mice, daily administration of pentoxifylline for the first four weeks post-transplant led to improved islet graft function

and an improved response to challenge with a glucose load¹³⁷.

Adverse effects include flushing (2.3%), nausea and emesis (~30%), headache, and dizziness. Mild reductions in blood pressure may also occur in some subjects. Concomitant administration of pentoxifylline with theophylline containing drugs can result in increased theophylline levels in some subjects. Its use is contraindicated in subjects with recent cerebral or retinal hemorrhages as it may increase the risk of bleeding.

5.4.4 Updated Vaccinations

Subjects will remain up to date on CDC-recommended adult vaccinations; please refer to the MOP for guidance.

5.4.5 Insulin Therapy

Glucose levels will be targeted to 80-120 mg/dL. Insulin (e.g., Regular®, Lispro®, NPH®, or Glargine®) will be administered as needed to maintain glucose levels in the target range. The subject will test BG five times per day (AM fasting, before lunch, 2 hours after lunch, before supper, and at bedtime). The subject's daily BG levels will be reviewed by a study nurse and/or one of the investigators three times per week during the first two weeks after discharge, and then weekly during the next month. Exogenous insulin will be withdrawn or adjusted as needed. Subjects will be considered insulin independent according to the definition of insulin independence.

5.4.6 Other Standard Therapies

Anti-hypertensive, anti-hyperlipidemia, and other approved therapies for pre-existing and new medical conditions will be provided per standard of care. Pre- and post-islet transplant procedure drug regimens (e.g., pre-transplant sedation and anesthetic) will be given per standard of care.

5.5 Rescue Medications

Rescue therapy will not be initiated in this protocol to treat suspected rejection. Immunologic surveillance methods that would allow diagnosis of islet allograft rejection early enough for timely intervention have yet to be identified and validated. If graft dysfunction is accompanied by biopsy proven rejection, the option for treatment will be discussed with the patient.

5.6 Prohibited Medications

Prohibited medications for this protocol, except as specifically indicated in this protocol include:

- Pramlintide acetate (Symlin®)
- Exenatide (Byetta®)
- Sulfonylureas (e.g., tolbutamide, tolazamide, chlorpropamide, glipizide, glyburide, glimepiride)
- Glitazides (e.g., repaglinide, nateglinide)
- Acarbose (Glucobay®, Precose®)
- Any medications in the macrolide antibiotic class other than Zithromax
- Other investigational products
- Immunomodulatory agents
- Other anti-diabetic agents
- Dapsone
- > 10 mg Prednisone (nasal steroids are allowed)

5.7 Assessment of Compliance with Study Treatment

Assessment of subject compliance will be determined by the completion of the scheduled study visits and required documentation that the specific subject is responsible for (e.g., Blood Sugar Records, AEs, and Insulin Use recording) as well as their willingness to comply with the recommendations of the study investigators. Any aberration of trough levels of immunosuppressive agents that could indicate nonadherence, lack of compliance that poses a significant clinical risk and or derangement of protocol data collection will be documented.

Please refer to Section 5.8.3 for a description of possible indications for premature discontinuation of study treatment.

5.8 Modification or Discontinuation of Study Treatment

5.8.1 Modification of Protocol Specific Drug(s)

Modification of certain protocol specific drugs, including etanercept, basiliximab, and rabbit ATG will be allowed in the event of complications.

5.8.2 Modification of Standard Immunosuppression

ISLETS ARE UNSUITABLE

Should an islet product become unsuitable for transplantation subsequent to induction immunosuppression, the subject will remain on maintenance therapy required for their renal transplant. This will provide sufficient time for organ procurement, islet isolation, and infusion of an islet product without any additional induction treatment to the recipient. An emergency request will be placed through UNOS that the next available pancreas for islet transplantation is directed to the selected manufacturing site. When an organ becomes available, investigators should defer to the MOP to determine the amount and type of induction immunosuppression that will be administered at the time of islet transplant.

GRAFT FAILURE

Subjects who experience islet graft failure will be maintained on their current immunosuppressive regimen for their renal graft as long as a subsequent islet transplant is possible. If/when it is determined that a subject will not receive a subsequent islet transplant, the subject will move to the reduced follow-up schedule.

ALLERGIC REACTION TO ATG

If a subject demonstrates an allergic reaction to thymoglobulin that results in cancellation of the initial transplant and the investigators feel that future use of the drug in the subject is contraindicated, the steps outlined should be followed. Once another organ becomes available, the subject will receive the alternate induction immunosuppressive regimen outlined in this protocol.

INTOLERANCE OF PROTOCOL MEDICATIONS

In the event that protocol-regulated concomitant medications are not tolerated, the subject will continue taking the immunosuppressive therapy in order to protect the islet and renal grafts. In the event that the immunosuppression regimen is not tolerated, the site PI may elect to prescribe an alternative immunosuppression regimen. The intent would be for the alternative regimen to be temporary in nature.

where possible and any such decision made with the primary interest of maintaining the function of the renal allograft. Any non-protocol directed study treatment modification that the site PI determines is necessary should be reported as a protocol deviation.

RABBIT ANTI-THYMOCYTE GLOBULIN-INDUCED ANAPHYLAXIS

In rare instances, anaphylaxis has been reported with Thymoglobulin® use. In such cases, the infusion should be terminated immediately. Medical personnel should be available to treat subjects who experience anaphylaxis. Emergency treatment such as 0.3 mL to 0.5 mL aqueous epinephrine (1:1000 dilution) subcutaneously and other resuscitative measures including oxygen, IV fluids, antihistamines, corticosteroids, pressor amines, and airway management, as clinically indicated, should be provided. Thymoglobulin® or other rabbit immunoglobulins should not be administered again for such subjects.

RABBIT ANTI-THYMOCYTE GLOBULIN-INDUCED CYTOKINE RELEASE

Thymoglobulin® infusion may cause cytokine release-related fever and chills. To minimize these, the first dose should be infused over a minimum of 6 hours into a high-flow vein. Also, premedication with corticosteroids (solumedrol, 1 mg/kg IV), pentoxifylline, acetaminophen, and/or an antihistamine will be provided in order to minimize the reaction incidence and/or intensity. At any sign of the above reaction, slowing the infusion rate by 50% will also occur.

NEUTROPENIA

Neutropenia is an expected consequence of the administration of several medications in this protocol. Subject safety is of utmost importance. Clinical treatment decisions take precedence over recommended guidelines.

If a subject's absolute neutrophil count is less than 1000 cells/ μ L and the subject is afebrile, then the following will be done:

- Reduce ATG by 50%.
- Test for CMV and if negative hold valganciclovir.
- Reduce trimethoprim/sulfamethoxazole to 80 mg/400 mg 3 times per week or hold trimethoprim/sulfamethoxazole.
- Review and obtain current sirolimus trough levels and consider dosage adjustment if trough levels are > 12 ng/dL (please refer to Appendix 1, SOE, for additional information).
- If subject is using mycophenolate mofetil or mycophenolate sodium in lieu of sirolimus, consider dose reduction.
- Consider administration of G-CSF.
- Monitor temperature BID.
- Follow-up within 48-72 hours to obtain repeat CBC with differential, subject symptoms, and measured temperatures.

If a subject's absolute neutrophil count is less than 1000 cells/ μ L and the subject is febrile, then the following will be done:

- Obtain Infectious Disease Consult.
- Obtain CMV antigenemia or PCR for CMV.
- Hold rabbit ATG.
- Hold valganciclovir and trimethoprim/sulfamethoxazole.
- Review and obtain current sirolimus trough levels and consider dosage adjustment if trough levels are > 12 ng/dL (please refer to Appendix 1, SOE, for additional information).
- If subject is using mycophenolate mofetil or mycophenolate sodium in lieu of sirolimus, consider dose reduction.

- Administer G-CSF.
- Monitor temperature BID.
- Follow-up within 48-72 hours to obtain repeat CBC with differential, subject symptoms, and measured temperatures.

If a subject's absolute neutrophil count is less than 500 cells/ μ L and the subject is afebrile, then the following will be done:

- Hold rabbit ATG.
- Hold administration of trimethoprim/sulfamethoxazole and/or valganciclovir.
- Review and obtain current sirolimus trough levels and hold dose if trough levels are > 12 ng/dL (please refer to Appendix 1, SOE, for additional information).
- If subject is using mycophenolate mofetil or mycophenolate sodium in lieu of sirolimus, consider holding dose.
- Obtain CMV antigenemia or PCR for CMV.
- Consider fluoroquinolones in afebrile subjects.
- Consider clotrimazole.
- Administer G-CSF.
- Monitor temperature BID.
- Follow up within 24 hours to obtain repeat CBC with differential, subject symptoms, and measured temperatures.

If a subject's absolute neutrophil count is less than 500 cells/ μ L and the subject is febrile, then the following will be done:

- The subject will be hospitalized under neutropenic precautions and an Infectious Disease/Hematology consult will be obtained.
- Hold rabbit ATG.
- Hold administration of trimethoprim/sulfamethoxazole and/or valganciclovir.
- Review and obtain current sirolimus trough levels and hold dose if trough levels are > 12 ng/dL (please refer to Appendix 1, SOE, for additional information).
- If subject is using mycophenolate mofetil or mycophenolate sodium in lieu of sirolimus, consider holding dose.
- Obtain CMV antigenemia or PCR for CMV.
- Administer G-CSF.

THROMBOCYTOPENIA

If the subject is found to have a platelet count (PLT) of $< 50 \times 10^9/L$, rabbit ATG will be withheld until PLT $> 50 \times 10^9/L$, then resume at a 50% reduced dose. If the PLT is $< 50 \times 10^9/L$, sirolimus will be withheld for 24 hours, then resume at a 50% reduced dose. If PLT fails to return to $> 50 \times 10^9/L$ within one week, sirolimus is to be withheld until PLT $> 50 \times 10^9/L$, after which sirolimus is resumed at 50% of the dose that preceded the drop in PLT to $< 50 \times 10^9/L$. If the PLT is between 50 and $75 \times 10^9/L$, reduce rabbit ATG dose by 50% until PLT is $> 75 \times 10^9/L$.

NEPHROTOXICITY

A sustained 33% increase in SCr warrants a prompt referral to a nephrologist for evaluation. Additionally, significant changes in renal function should be reported to the patient's physician managing the renal transplant. If it is thought that the decrease in renal function is attributable to CNI immunosuppressive therapy, the physician managing the renal transplant should consider ONE of the therapeutic alternatives shown in Table 3.

Table 3. Immunosuppressive Medication Modifications

Allowable therapeutic responses to CNI- induced nephrotoxicity	Rationale
Discontinue sirolimus, and replace it with mycophenolate mofetil or mycophenolate sodium	The nephrotoxic effect of CNIs is increased by concomitant administration of sirolimus.
If the trough sirolimus level is maintained at >10 ng/mL without adverse effects, discontinue the CNI and replace it with mycophenolate mofetil or mycophenolate sodium.	CNI should be discontinued only if the subject can tolerate a trough level of sirolimus that will result in adequate immunosuppression.
Decrease the target CNI trough level by 25%	CNI toxicity is dose-related

Anti-hypertensives, anti-hyperlipidemics, and other preferred therapies for preexisting and new medical conditions will be provided per standard of care.

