1.5.3.2 Rabbit Anti-Thymocyte Globulin (Thymoglobulin®)

Rabbit ATG (Thymoglobulin®) was approved by the FDA in 1999 for the treatment for acute renal graft rejection in conjunction with concomitant immunosuppression (see Thymoglobulin® package insert for details). It is a polyclonal IgG antibody obtained by immunization of rabbit with human thymocytes, and contains cytotoxic antibodies directed against antigens expressed on human T lymphocytes. Thymoglobulin® has shown a consistent safety profile with most AEs being manageable and reversible; the most common events are fever, chills, and leukopenia. While rare, the most severe events include allergic or anaphylactoid reactions and serum sickness. As with all immunosuppression, administration of Thymoglobulin® may be associated with an increased risk of infection and development of malignancy (especially of the skin and lymphoid system).

In 82 kidney transplant recipients receiving 1.5 mg/kg/day for 7 - 14 days, the principal AEs were fever (52%) and chills (47%) associated with the infusions, leukopenia (47%), and thrombocytopenia (30%). CMV infection occurred in 13% and PTLD in 2% of subjects. Neutropenia has been described; anaphylaxis has been reported rarely.

Published results of the use of Thymoglobulin® in clinical and experimental islet transplantation are limited to relatively small cohorts. Hirshberg et al described the successful role of rabbit ATG and sirolimus in reducing rejection of islet allografts in primates, with no evidence of direct islet toxicity from Thymoglobulin®²⁹. Hering et al described a beneficial role of Thymoglobulin® induction (6 mg/kg) in 8 subjects with T1D receiving single donor islet grafts, all of whom achieved insulin independence and were protected against recurrence of hypoglycemia⁹². Acute islet rejection was described in subjects receiving calcineurin-free immunosuppression when sirolimus levels fell below 9 ng/mL. The use of higher doses of sirolimus exacerbated the neutropenic side effects of Thymoglobulin®, but these could be managed safely without risk of opportunistic infections when appropriate dose reduction and/or administration of Granulocyte Colony Stimulating Factor (G-CSF; Neupogen®) is utilized⁹².

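### Section 5.8.2 prints the sirolimus trough trigger for neutropenia in ng/dL instead of ng/mL, so the level test has no effect for subjects with a stated sirolimus target

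*Combined protocol and SAP*

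**What the plan says.** The neutropenia part of section 5.8.2 has four tiers, defined by neutrophil count (below 1000 or below 500 cells/μL) and by the absence or presence of fever. Each tier asks for a current sirolimus trough and ties an action to it.

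- Below 1000, afebrile and febrile: "consider dosage adjustment if trough levels are > 12 ng/dL".
- Below 500, afebrile and febrile: "Review and obtain current sirolimus trough levels and hold dose if trough levels are > 12 ng/dL".

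The same limit and unit therefore appear four times. The part opens with a general override: "Clinical treatment decisions take precedence over recommended guidelines".

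Other places give sirolimus levels on a different scale. Table 3, also in section 5.8.2, allows a change of regimen "If the trough sirolimus level is maintained at >10 ng/mL without adverse effects". Section 1.5.3.2 reports acute islet rejection, on regimens without a calcineurin inhibitor, "when sirolimus levels fell below 9 ng/mL". Section 7.4 gives a sirolimus target of 3-15 for subjects on tacrolimus plus sirolimus. No unit follows that figure, but the tacrolimus target beside it, 3-10, is in ng/mL, and the two levels are to sum to 12-20.

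**The concern.** The trigger governs a drug dose, and its unit does not match the scale that the protocol uses for the same drug elsewhere. If ng/dL is taken at face value, the limit is so low that any trough in the stated target range passes it. The condition then separates nobody: an instruction to hold the drug when the level is high becomes an instruction to hold it.

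At stake is the maintenance immunosuppression of a neutropenic subject who already carries a kidney graft and an islet graft. The protocol calls neutropenia an expected consequence of several of its medications, so these tiers are likely to be consulted.

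**Working it through.** **What can be reproduced.** The trigger is printed, not derived. There is no calculation of the plan's to repeat; the check is a unit conversion and a comparison with the protocol's other sirolimus levels.

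**Inputs**

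- Trigger: above 12 ng/dL, four times (section 5.8.2, neutropenia).
- Level for the regimen change: above 10 ng/mL (section 5.8.2, Table 3).
- Level in the risk text: 9 ng/mL (section 1.5.3.2).
- Targets for tacrolimus plus sirolimus: tacrolimus 3-10 ng/mL, sirolimus 3-15 with no unit, combined 12-20 (section 7.4).

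**Step 1: convert the trigger.** 1 dL = 100 mL, so 12 ng/dL = 12 / 100 = 0.12 ng/mL. This is 100-fold below 12 ng/mL.

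**Step 2: settle the unit of the 3-15 target.**

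- If it were ng/dL, 3-15 would be 0.03-0.15 ng/mL. The largest possible sum with tacrolimus would be 10 + 0.15 = 10.15 ng/mL, below the combined floor of 12. No subject could meet the combined target.
- If it is ng/mL, the sum runs from 3 + 3 = 6 to 10 + 15 = 25 ng/mL, which covers 12-20.

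Only ng/mL is consistent with section 7.4.

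**Step 3: compare levels with the printed trigger of 0.12 ng/mL.**

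| Sirolimus level | ng/mL | Multiple of trigger |
|---|---|---|
| Lower end of target (7.4) | 3 | 3 / 0.12 = 25 |
| Risk text (1.5.3.2) | 9 | 9 / 0.12 = 75 |
| Table 3 | 10 | 10 / 0.12 ≈ 83 |
| Upper end of target (7.4) | 15 | 15 / 0.12 = 125 |

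Every trough from 3 to 15 ng/mL exceeds the printed trigger.

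**Step 4: read the tiers literally.** For a subject on tacrolimus plus sirolimus with an on-target trough, sirolimus is held at a count below 500, and adjustment is considered at a count below 1000, whatever the level. With 12 ng/mL, the test would again separate troughs above 12 from those at or below it.

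**Step 5: was a level-free rule intended?** The wording suggests not. Where the authors want a hold without a level test they write one: for platelets below 50 × 10⁹/L, "sirolimus will be withheld for 24 hours, then resume at a 50% reduced dose". The mycophenolate bullets in the neutropenia tiers likewise carry no level condition. The sirolimus bullets do carry one, and the unit cancels it.

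**Step 6: does another section supply the unit?** The bullets refer to the schedule in Appendix 1. As it can be read, that schedule has a row for calcineurin inhibitor levels and none for sirolimus troughs, so it does not settle the matter.

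**The case against.** The strongest reply is that this is a slip of the pen with almost no practical effect. A transplant clinician would probably recognise it, since Table 3 in the same section uses ng/mL. The override clause lets clinical judgement prevail, and two of the four tiers only ask for an adjustment to be considered. The literal error also points toward less of a drug about which section 1.5.3.2 says: "The use of higher doses of sirolimus exacerbated the neutropenic side effects". All of this stands, and it fixes the severity. It does not make the printed limit right: an override clause does not replace a correct number.

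A reader might infer more than the documents support, in three ways.

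- **That the trigger catches every on-target sirolimus user.** Sirolimus is also allowed with cyclosporine. For that combination section 7.4 gives a combined trough or a 2-hour level, with no separate sirolimus target, so being on target for sirolimus is undefined there. The treating physician may also adjust target levels. The statement holds for tacrolimus plus sirolimus at the stated target.
- **That a literal hold could leave a subject without maintenance immunosuppression.** Table 3 does let the calcineurin inhibitor be stopped, under the caution that "CNI should be discontinued only if the subject can tolerate a trough level of sirolimus" giving adequate immunosuppression. But it also requires replacement with a mycophenolate product, so a sirolimus hold would not by itself remove all cover. The rejection reported in section 1.5.3.2 is useful here for its unit; it comes from another cohort.
- **That 12 is also the wrong number, because 12 ng/mL lies inside the 3-15 target.** A neutropenia rule may properly act within a target range, and nothing in the documents points to another value.

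**Conclusion.** The unit is wrong as written in all four neutropenia tiers, by a factor of 100. For subjects on tacrolimus plus sirolimus, the only group with a stated sirolimus target, the whole target range lies 25 to 125 times above the printed trigger, and the level test has no effect.

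The conclusion rests on two readings. The first is that the 3-15 target is in ng/mL, which the combined target of 12-20 forces. The second is that a working level test was intended, which the wording of the neighbouring rules supports. Misreading of the PDF is an unlikely explanation: the same string occurs four times, and ng/mL is legible in Table 3 soon after.

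Severity is minor. Only sirolimus users who become neutropenic are reached, and the documents do not allow their number to be computed. A reader might suspect an effect on the trial's results, but no endpoint, power or analysis figure depends on this limit.

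**What to change.** In section 5.8.2, change ng/dL to ng/mL in the four neutropenia bullets. In section 7.4, print ng/mL after the sirolimus target of 3-15, so that the trigger and the target visibly share one scale. The cost is one unit corrected in four places and one unit added, with no further assays, visits or analyses.
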